1.13.2 Local injection site tolerability

Local injection site tolerability will be assessed on the injection site (separately from the adverse event page). Each patient will be classified into one of the following four categories (based on AE ATC grade):

1. No tolerability reactions at any time in the trial.
2. A mild reaction (grade 1) observed on at least one occasion but no moderate or severe/ potentially life threatening reactions.
3. A moderate reaction (grade 2) observed on at least one occasion but no severe/ potentially life threatening reactions.
4. A severe (grade 3) or potentially life threatening (grade 4) reaction observed on at least one occasion.

The number and percentage of patients in each category will be presented for each cohort, epoch, initial randomized treatment and treatment sequence (as defined in [section 1.3](#)). In addition, summary of pre-specified symptoms (Erythema/Redness, Tenderness, Induration/Swelling, Pain) will be provided. All details of injection site reactions will be listed.

1.13.3 Laboratory data

Laboratory parameters will be summarized by presenting descriptive statistics for the absolute values, change from baseline (and from each start of epoch) for each cohort, epoch, analysis visit and treatment group (as defined in [section 1.3](#)). Change from baseline (resp. start of epoch) will only be summarized for patients with both baseline (resp. start of epoch) and post baseline values in each epoch. There will be multiple "baseline" as one will be defined for each start of epoch. All information collected will be listed by patient and abnormal values will be flagged. In addition, shift tables based on normal ranges and incidence rates of notable abnormalities will be presented.

Creatinine clearance will be also be summarized by subgroup of Colchicine for crFMF disease cohort. Creatinine clearance will also be summarized by subgroup of CKD categories defined at baseline derived using eGFR value as below:

CKD Stage 1: ≥ 90 ml/min/1.73m²

CKD Stage 2: $60 - < 90$ ml/min/1.73m²

CKD Stage 3a-b: $30 - < 60$ ml/min/1.73m²

CKD Stage 4-5: < 30 ml/min/1.73m²

Shift in CKD stage from baseline to end of epoch 2, epoch 3 and epoch 4 will be summarized for crFMF disease cohort patients.

Notable laboratory abnormalities in adult patients (≥ 18 years of age)

Post-baseline values will be flagged as notable abnormalities as follows:

Biochemistry

1. ALT (SGPT): $> 3x, 5x, 10x$, and $20x$ Upper Limit of Normal (ULN)₁
2. AST (SGOT): $> 3x, 5x, 10x$, and $20x$ ULN₁
3. Elevation of AST and/ or ALT ($> 3x$ ULN) accompanied by elevated bilirubin ($> 1.5x$ ULN, $> 2x$ ULN)₁
4. Any elevations of bilirubin; elevated total bilirubin (TBL) to $> 2x$ ULN₁
5. Any elevations of ALP $> 1.5x$ ULN
6. Gamma-Glutamyltransferase (GGT): $> 3x$ ULN
7. Creatinine (serum): $\geq 3x$ ULN
8. Creatinine clearance (CrCl) (Cockcroft-Gault formula)₂: $\geq 25\%$ decrease from baseline
9. Triglycerides: $> 5x$ ULN

Hematology

1. Hemoglobin: ≥ 20 g/L decrease from baseline,
 < 100 g/L
2. Platelet count:
 - a. CTC Grade 1: $<$ Lower Limit of Normal (LLN) – 75×10^9 /L
 - b. CTC Grade 2: $< 75 - 50 \times 10^9$ /L
 - c. CTC Grade 3: $< 50 - 25 \times 10^9$ /L
 - d. CTC Grade 4: $< 25 \times 10^9$ /L
3. White blood cell count:
 - a. CTC Grade 1: $<$ LLN – 3×10^9 /L
 - b. CTC Grade 2: $< 3 - 2 \times 10^9$ /L
 - c. CTC Grade 3: $< 2 - 1 \times 10^9$ /L
 - d. CTC Grade 4: $< 1 \times 10^9$ /L
4. Absolute neutrophils:
 - a. CTC Grade 1: $<$ LLN – 1.5×10^9 /L

- b. CTC Grade 2: $<1.5 - 1 \times 10^9/L$
- c. CTC Grade 3: $<1 - 0.5 \times 10^9/L$
- d. CTC Grade 4: $<0.5 \times 10^9/L$

5. Absolute lymphocytes: $<LLN$

6. Absolute eosinophils: $\geq 2.5x, \geq 3x ULN$

Urinalysis

Protein urine dipstick: $\geq ++$

Notable laboratory abnormalities in pediatric patients (< 18 years of age)

Post-baseline values in pediatric patients (at the time of the assessment) will be flagged as notable abnormalities as follows:

Biochemistry

1. ALT (SGPT): $> 3x, 5x, 10x, \text{ and } 20x$ Upper Limit of Normal (ULN)¹
2. AST (SGOT): $> 3x, 5x, 10x, \text{ and } 20x$ ULN¹
3. Elevation of AST and/ or ALT ($> 3xULN$) accompanied by elevated bilirubin ($> 1.5xULN, > 2xULN$)¹
4. Any elevations of bilirubin; elevated total bilirubin (TBL) to $> 2x$ ULN¹
5. Any elevations of ALP $>1.5x$ ULN¹
6. GGT: $\geq 3x, 5x$ ULN
7. Creatinine (serum): $\geq 1.5x$ ULN
8. Creatinine clearance (Schwartz formula[§]): $\geq 25\%$ decrease from baseline, ≥ 2 consecutive visits
9. Total Cholesterol: $\geq 1.5xULN$
10. Triglycerides: ≥ 5.7 mmol/L
11. Creatinine clearance (Schwartz formula⁴): $\geq 25\%$ decrease from baseline for ≥ 3 months in duration in combination with protein urine dipstick resulting in new protein $\geq 1+, \geq 3$ months in duration

Hematology

1. Hemoglobin: ≥ 20 g/L decrease from baseline,
 <85 g/L (patients < 16 years of age) or <100 g/L (patients ≥ 16 years of age)
2. Platelet count
 - CTC Grade 1: $<$ Lower Limit of Normal (LLN) – $75 \times 10^9/L$
 - CTC Grade 2: $<75 - 50 \times 10^9/L$
 - CTC Grade 3: $<50 - 25 \times 10^9/L$
 - CTC Grade 4: $<25 \times 10^9/L$
3. White blood cell count
 - CTC Grade 1: $<LLN - 3 \times 10^9/L$
 - CTC Grade 2: $<3 - 2 \times 10^9/L$

- CTC Grade 3: $<2 - 1 \times 10^9/L$
- CTC Grade 4: $<1 \times 10^9/L$

4. Absolute neutrophils

- CTC Grade 1: $<LLN - 1.5 \times 10^9/L$
- CTC Grade 2: $<1.5 - 1 \times 10^9/L$
- CTC Grade 3: $<1 - 0.5 \times 10^9/L$
- CTC Grade 4: $<0.5 \times 10^9/L$

5. Absolute lymphocytes: $<LLN$

6. Absolute Eosinophils: $\geq 1.1 \times ULN, \geq 0.45 \times 10^9/L$

Urinalysis

- Protein urine dipstick: $\geq +$ for ≥ 3 months in duration

¹ Adapted from FDA Guidance for Industry Drug-Induced Liver Injury: Premarketing Clinical Evaluation (July 2009)

² Cockcroft-Gault formula (Men): $CrCl \text{ (mL/min)} = [((140 - \text{age (years)}) \times \text{weight (kg)}) / (\text{serum creatinine } (\mu\text{mol/L}) / 88.4) \text{ (mg/dL)} \times 72]$

² Cockcroft-Gault formula (Women): $CrCl \text{ (mL/min)} = [((140 - \text{age (years)}) \times \text{weight (kg)}) / (\text{serum creatinine } (\mu\text{mol/L}) / 88.4) \text{ (mg/dL)} \times 72] \times 0.85$

³ Common Terminology Criteria for Adverse Events, US Department of Health and Human Services (v4.03: 14-Jun-2010)⁴ Creatinine clearance was derived using the following formula:

$CrCl \text{ (mL/min/1.73m}^2\text{)} = [0.413 \times \text{length (cm)} / (\text{serum creatinine mg/dl})] \text{ (Schwartz et al. 2009).}$

1.13.4 Vital signs

Vital signs will be summarized by presenting descriptive statistics for the absolute values and changes from baseline (and from each start of epoch) for each cohort, epoch, analysis visit and treatment group (as defined in [section 1.3](#)). All information collected will be listed by patient and abnormal values will be flagged

Notable vital signs abnormalities in adult patients (≥ 18 years of age)

Post-baseline vital signs will be flagged as notable abnormalities as follows:

1. Systolic/Diastolic blood pressure: $\geq 25\%$ decrease or $\geq 25\%$ increase from baseline
2. Pulse: ≥ 110 bpm with $\geq 15\%$ change from baseline, or < 50 bpm with $\geq 15\%$ change from baseline

Notable vital signs abnormalities in pediatric patients (< 18 years of age)

Post-baseline vital signs in pediatric patients (at the time of the assessment) will be flagged as notable abnormalities as follows:

1. Systolic blood pressure (mmHg): >ULN and increased >20 in change from baseline or <LLN and decreased >20 in change from baseline
2. Diastolic blood pressure (mmHg): >ULN and increased >20 in change from baseline or <LLN and decreased >20 in change from baseline
3. Pulse (bpm): >ULN and increased >20 in change from baseline or <LLN and decreased >20 in change from baseline

Blood pressure normal range for patients >28 days but <18 years old are listed in below table:

Table 1-3 Blood pressure normal range in pediatric population according to current age

Age	SBP	DBP	Pulse
0 - 1 months[#]	45-80	33-52	93-182
>1 - 3 months[#]	65-85	35-55	120-178
>3 - 6 months[#]	70-90	35-65	107-197
>6 -12 months[#]	80-100	40-65	108-178
>12 months- 2 years[#]	80-100	40-70	90-152
> 2 years - 5 years	100-115	65-75	80-130
> 5 years -12 years	110-125	70-80	70-115
> 12 years -18 years	120-135	75-85	60-100

Age is age at the time of the visit.

[#]Reference values according to website: <http://www.sickkids.ca/Nursing/Education-and-learning/Nursing-Student-Orientation/module-two-clinical-care/vitals/>.

ECG

Listings and table will be provided for notable ECG abnormalities. Summary statistics will be presented for ECG variables by epoch, analysis visit and treatment group for each cohort.

1.13.5 Immunogenicity

A listing for each cohort will be presented for patients who develop immunogenicity.

1.13.6 Liver safety monitoring

A listing for each cohort will be presented for patients with liver events.

1.14 Interim analyses

Contingency Analysis

If there is any delay in the enrollment of the patients in one of the cohorts in the randomized treatment epoch i.e. it takes more than 24 weeks to recruit patients in one of the cohorts, then an interim analysis performed within each cohort would be considered. The decision to perform

this interim analysis would be taken jointly between the indication-specific lead investigators and Novartis.

- If overall enrollment time has surpassed 24 weeks,
- AND If >2/3 patients are enrolled in the slowest enrolling cohort.

However, due to the low number of patients in the slowest enrolling cohort, the interim analysis will not be sufficiently powered to detect statistically significant differences. Thus only descriptive analysis would be performed in this cohort and these results will complete the dossier with the final results of the two cohorts where all patients have been recruited.

Primary efficacy analysis

In order to support regulatory filing, the analyses of the primary and all Week 16 secondary efficacy variables will be performed after all subjects have completed the final visit of the randomized treatment epoch (Epoch 2) of the study (Day 113). These results will be presented in a first Clinical Study Report (CSR).

40-week interim analysis

An interim analysis is planned at the end of the randomized withdrawal epoch (Epoch 3). An Interim Analysis CSR may be prepared to support health authority interactions, as necessary. The final long-term safety analyses involving data from all 4 epochs will be performed after all patients have completed the final visit of the trial (Day 785) and will be presented in the final CSR.

1.15 Determination of sample size

The primary efficacy objective in the randomized treatment epoch and for the overall study is to compare canakinumab treatment to placebo with respect to the proportion of responders at Week 16 using the Fisher's exact test. The proportion of responders, as well as the odds ratio (if estimable) and risk difference with corresponding 97.5% confidence interval will be presented.

Since a 20% screening failure rate is expected, it is estimated that approximately [REDACTED] patients have to be screened.

Nquery Advisor® software version 7.0 was used.

2 Clinical Study Report - Appendix 16.1.9 Documentation of statistical methods

2.1 Analysis visit windows

Baseline/ First day in Epoch 2

For canakinumab naïve Japanese crFMF patients with non-exon 10 mutations and patients >28 days but <2 years old, the date of baseline is equal to the first date of dosing.

For patients who are randomized in epoch 2 then date of baseline is equal to the first date of dosing on or after the date of randomization (Visit 101).

For laboratory and vital signs evaluations the latest value before start of treatment in Epoch 2 was taken as baseline in case of missing baseline.

First day in Epoch 3

For patients who roll-over from study ACZ885D2203/D2207M, the date of baseline is equal to the first date of dosing.

For canakinumab patients in epoch 2 who are responder at week 16, the first day in epoch 3 is equal to the first date of dosing on or after the date of re-randomization (Visit 201).

For the other patients, the first day in epoch 3 is equal to the first date of dosing at visit 201.

First day in Epoch 4

For all patients, the first day in epoch 4 is equal to the first date of dosing at visit 301.

Time visit window

The visit numbers as reported in the CRF were used except for end of study/epoch visit (visit=199, 299, 399), which were mapped according to Table 2-1.

Table 2-1 Visit window definition

Epoch	Analysis Visit	Visit window (days) for patients who entered epoch 2	Visit window (days) for patients who directly entered epoch 3
2	Day 15 (Week 3)	2 – 18	–
2	Day 29 (Week 5)	19 – 32	–
2	Day 57 (Week 9)	33 – 60	–
2	Day 85 (Week 13)	61 – 88	–
2	Day 113 (Week 17)	89 – 116	–
3	Day 141 (Week 21)	117 – 144	2 – 32
3	Day 169 (Week 25)	145 – 172	33 – 60
3	Day 197 (Week 29)	173 – 200	61 – 88
3	Day 225 (Week 33)	201 – 228	89 – 116
3	Day 253 (Week 37)	229 – 256	117 – 144
3	Day 281 (Week 41)	257 – 284	145 – 172
4	Day 337 (Week 49)	285 – 340	173 – 228
4	Day 393 (Week 57)	341 – 396	229 – 284
4	Day 449 (Week 65)	397 – 452	285 – 340
4	Day 505 (Week 73)	453 – 508	341 – 396
4	Day 561 (Week 81)	509 – 564	397 – 452
4	Day 617 (Week 89)	565 – 620	453 – 508
4	Day 673 (Week 97)	621 – 676	509 – 564
4	Day 729 (Week 105)	677 – 732	565 – 620
4	Day 785 (Week 113)	>733	>620

For subjects who prematurely discontinue between two scheduled visits, the data at the end of study/epoch visit will be re-aligned to the visit which belongs to the associated visit window. If the early termination visit is mapped to a visit for which the scheduled visit was already performed, then the assigned visit number will be set to the next one. For example if a patient discontinued prematurely at week 8 (assigned based on the visit window above) but already has a value for week 8, then the end of study visit will be set to week 12.

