5.5.14 Early study termination

The study can be terminated at any time for any reason by Novartis. Should this be necessary, the patient should be seen as soon as possible and treated for a prematurely withdrawn patient. The investigator may be informed of additional procedures to be followed in order to ensure that adequate consideration is given to the protection of the patient's interests. The investigator will be responsible for informing the Institutional Review Board/Independent Ethics Committee (IRBs/IECs) of the early termination of the trial.

6 Visit schedule and assessments

[Table 6-1](#) (screening epoch [Epoch 1] and the randomized treatment epoch [Epoch 2]) and [Table 6-2](#) (randomized withdrawal epoch [Epoch 3] and open-label treatment epoch [Epoch 4]) list all of the assessments and indicate with an “x” when the visits are performed.

Patients are to be seen for all visits, preferably on the designated day. The proposed visit day is displayed in [Table 6-1](#) and [Table 6-2](#).

Patients who prematurely withdraw from Epoch 2 for any reason should be scheduled for a visit when all the assessments listed for Day 113 will be performed.

Patients who prematurely withdraw from Epoch 3 for any reason should be scheduled for a visit when all the assessments listed for Day 281 will be performed.

Patients who prematurely withdraw from Epoch 4 for any reason should be scheduled for a visit when all the assessments listed for Day 785 will be performed.

If a patient refuses to return for these assessments or is unable to do so, every effort should be made to contact him/ her by telephone to determine the reason for discontinuation.

At a minimum, patients will be contacted for safety evaluations and a follow-up visit or phone call for SAEs must be performed 30 days following Investigational treatment discontinuation (TD), Premature subject withdrawal (PSW) or 8 weeks after last injection of study drug, whichever is later.

Documentation of attempts to contact the patient should be recorded in the patient record.

**Table 6-1 Assessment schedule:
Screening epoch (Epoch 1) and randomized treatment epoch (Epoch 2)**

Epoch	Screening (Epoch 1)	Randomized treatment epoch (Epoch 2)						
Visit	1	101	102	103	104	105	199 and/ or PSW	Safety follow-up
Week		1	3	5	9	13	17	
Day	-84 to -3	1	15	29	57	85	113	PSW +30 or 8 weeks after last injection¹
Informed consent	X							
Informed consent for pharmacogenetic sampling ²	X							

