1.10.2.1 Testing strategy

The following hypotheses will be included in the closed testing procedure, and type-I-errors will be set such that a family-wise type-I-error rate of 2.5% is kept (one sided tests)

- Primary objective: H_1 .

Secondary objectives:

- H_2 : Canakinumab 150mg q4w is not different to placebo with respect to the percentage of patients with PGA < 2 at Week 16.
- H_3 : Canakinumab 150mg q4w is not different to placebo with respect the percentage of patients with CRP ≤ 10 mg/L at Week 16.
- H_4 : Canakinumab 150mg q4w is not different to placebo with respect the percentage of patients with SAA ≤ 10 mg/L at Week 16.
- H_5 : Canakinumab 150mg q8w is not different to placebo with respect to the percentage of responders (absence of new flares) at Week 40.

If the primary objective is achieved, all secondary endpoints in the randomized treatment epoch (Epoch 2) will be assessed. If all secondary objectives are achieved in the randomized treatment epoch (Epoch 2), then the secondary objective in the randomized withdrawal epoch will be tested. The 95% confidence interval for the proportions will be calculated using exact (Clopper-Pearson) method.

Physician's global assessment of disease activity (PGA)

PGA is based on a 5-point scale for disease associated signs and symptoms:

0 (=none/no), 1 (=minimal), 2 (=mild), 3 (=moderate), and 4 (severe).

Frequency tables will be provided by analysis visit and randomized treatment groups for each cohort. Between-treatment differences for the proportion of patients with $\text{PGA} < 2$ at Week 16 will be analyzed using a logistic regression model with treatment group, and baseline PGA as explanatory variables for each cohort. All randomized patients at start of Epoch 2 will be considered for this analysis. Patients needing dose escalation in the canakinumab arms, or who escape from placebo arms to canakinumab in the randomized treatment epoch (Epoch 2), or discontinued from the study due to any reason prior evaluating the endpoint at week 16, will be considered as having $\text{PGA} \geq 2$. If the logistic regression model has difficulty converging due low or high response rates, then Firth's method will be used in the logistic regression model. If the convergence issue is still not resolved then Canakinumab treatment group will be compared to placebo with respect to the proportion of patients with $\text{PGA} < 2$ at Week 16 will be analyzed using the Fisher's exact test.

Serological remission

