Serological remission is defined as $\text{CRP} \leq 10\text{mg/L}$. Between-treatment differences for the proportion of patients with $\text{CRP} \leq 10\text{mg/L}$ at Week 16 will be analyzed using a logistic regression model with treatment group, and baseline CRP values as explanatory variables for each cohort. All randomized patients at Epoch 2 will be considered for this analysis. Patients needing dose escalation in the canakinumab arms, or who crossed-over from placebo arms to canakinumab in the randomized treatment epoch (Epoch 2), or discontinued from the study due to any reason prior evaluating the endpoint at week 16, will be considered as having $\text{CRP} > 10\text{mg/L}$. If the logistic regression model has difficulty converging due low or high response rates, then Firth's method will be used in the logistic regression model. If the convergence issue is still not resolved then the canakinumab treatment group will be compared to placebo with respect to the proportion of patients with $\text{CRP} \leq 10\text{mg/L}$ at Week 16 will be analyzed using the Fisher's exact test.

Normalization of SAA

Normalization of SAA is defined as $\text{SAA} \leq 10\text{mg/L}$. Between-treatment differences for the proportion of patients with $\text{SAA} \leq 10\text{mg/L}$ at Week 16 will be analyzed using a logistic regression model with treatment group, and baseline SAA values as effect for each cohort. All randomized patients at Epoch 2 will be considered for this analysis. Patients needing dose escalation in the canakinumab arms, or who crossed-over from placebo arms to canakinumab

in the randomized treatment epoch (Epoch 2), or discontinued from the study due to any reason prior evaluating the endpoint at week 16, will be considered as having SAA > 10mg/L. If the logistic regression model has difficulty converging due low or high response rates, then Firth's method will be used in the logistic regression model. If the convergence issue is still not resolved then the Canakinumab treatment group will be compared to placebo with respect to the proportion of patients with SAA ≤ 10mg/L at Week 16 will be analyzed using the Fisher's exact test.

Maintenance of clinically meaningful response

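### Read literally, SAP 2.1 gives no Week 16 PGA, CRP or SAA value to a completer whose Visit 199 falls on Day 117 or later, and no rule for H2 to H4 covers that patient

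*SAP*

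**What the plan says.** SAP 2.1 (Analysis visit windows) uses the visit numbers reported in the CRF, "except for end of study/epoch visit (visit=199, 299, 399), which were mapped according to Table 2-1". That sentence is not restricted to patients who withdrew. Table 2-1 gives the Day 113 visit, which it counts as Week 17 and which is the Week 16 endpoint visit under SAP 1.14, a window of Days 89 to 116. Days 117 to 144 belong to Day 141 and Days 145 to 172 to Day 169, both in Epoch 3. Days are counted from the first dose on or after randomization.

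The paragraph after the table describes a narrower use: "For subjects who prematurely discontinue between two scheduled visits, the data at the end of study/epoch visit will be re-aligned" to the visit whose window contains them.

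Protocol Table 6-1 labels the Day 113 column as Visit 199 and/or PSW, so one visit number serves completers and withdrawals. Protocol Section 6 sets no numeric tolerance: "Patients are to be seen for all visits, preferably on the designated day".

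For H2, SAP 1.10.2.1 states: "All randomized patients at start of Epoch 2 will be considered for this analysis". For H3 and H4 it states: "All randomized patients at Epoch 2 will be considered for this analysis". Failure is imputed after dose escalation in the canakinumab arm, after escape or cross-over from placebo, and for a patient who "discontinued from the study due to any reason prior evaluating the endpoint at week 16, will be considered as having" the unfavourable outcome.

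**The concern.** A patient who finishes Epoch 2 on randomized treatment and attends the closing visit four days late is not a discontinuer, an escalation or a cross-over. Under the literal mapping, the PGA, CRP and SAA from that visit are filed under an Epoch 3 visit and the Week 16 cell is empty. The SAP does not say whether such a patient drops out of the logistic model or counts as a failure. Dropping the patient contradicts the statement that all randomized patients are considered. Counting the patient as a failure has no basis in the listed rules.

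H2 to H4 are confirmatory, and all must succeed before H5 is tested. The loss is also selective. Patients who escaped or discontinued are failures by rule whatever their visit day, so only patients still on randomized treatment can lose a value. If canakinumab works, more of these are canakinumab patients and many are successes.

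**Working it through.** **1. Table 2-1 applied as written.** Every bounded window in the Epoch 2 column ends three days after its target: 15 + 3 = 18, 29 + 3 = 32, 113 + 3 = 116, 281 + 3 = 284. Each window starts the day after the previous one ends. For Day 113 the reach is 113 − 89 = 24 days early and 116 − 113 = 3 days late.

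| Day of Visit 199 | Analysis visit |
|---|---|
| 89 to 116 | Day 113, Epoch 2 |
| 117 to 144 | Day 141, Epoch 3 |
| 145 to 172 | Day 169, Epoch 3 |

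A closing visit 24 days early keeps the Week 16 label and one 4 days late loses it. That suits the placing of an early-termination visit. It does not suit a tolerance for a scheduled visit. Visit 299 has the same limit: Day 284 maps to Day 281, and Day 285 maps to Day 337 in Epoch 4.

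**2. Is the value recovered elsewhere?** The failure rules for H2 to H4 name three events, none of which describes a late completer. The substitution in SAP 1.10.1.1 replaces a missing local CRP by the central CRP; it does not change the visit. The SAP names no other visit as a source for Week 16.

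**3. How many patients?** The documents give no spread of visit days, so this step is assumption. Take the day of Visit 199 as normal around Day 113. With whole days, the share on Day 117 or later is P(Z > 3.5/SD).

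| Assumed SD (days) | Share on Day 117 or later | Ceiling per cohort of 60 (60 × share) |
|---|---|---|
| 2 | 4.0% | 2.4 |
| 3 | 12.2% | 7.3 |
| 5 | 24.2% | 14.5 |
| 7 | 30.9% | 18.5 |

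The last column assumes that all 60 patients of a cohort (Protocol Section 4) complete on randomized treatment. The real count is smaller, because escaped and discontinued patients are failures already.

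**4. Effect on one arm (illustration).** Suppose 20 of 30 canakinumab patients truly have PGA below 2 at Week 16 and 4 of the 20 are seen late.
- All values kept: 20/30 = 66.7%
- Late completers dropped: 16/26 = 61.5%
- Late completers counted as failures: 16/30 = 53.3%

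**5. Would the test change?** One-sided Fisher tests stand in here for the planned logistic model, with assumed placebo successes out of 30 and no late placebo successes.

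| Placebo | 20/30 | 16/26 | 16/30 |
|---|---|---|---|
| 6/30 | 0.0003 | 0.0017 | 0.0075 |
| 8/30 | 0.0020 | 0.0088 | 0.032 |

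With 2 to 6 placebo successes, every version stays below 0.025, and 0.0075 is the largest value. At 8 of 30, only the version that counts late completers as failures crosses the limit.

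**The case against.** The strongest reply is that SAP 2.1 must be read as a whole. The paragraph after Table 2-1 speaks only of premature discontinuers and early-termination visits, and its example is a discontinuer. Nothing there maps a completer. SAP 2.1 starts Epoch 3 at the first dosing at Visit 201, and SAP 1.14 ties the Week 16 analysis to completion of the closing Epoch 2 visit without a calendar limit. On this view the text is only loosely drafted. Much of this stands as evidence of intent. It does not narrow the mapping sentence, which a programmer could apply to every Visit 199 and 299 record.

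The assumed spread and the choice of 4 late patients are fair targets too. So is the lack of a demonstrated change in any test result: step 5 needs several unfavourable assumptions together. The body of Table 6-2 is not legible in the text available, so whether Visit 201 repeats these assessments could not be checked.

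A reader might infer more than the documents support:
- **Flares at a late Visit 199 or 299 move to the next epoch and distort H1 or H5.** No section assigns flares through Table 2-1. H1 counts flares over the 16 weeks after randomization, and H5 counts flares between Week 16 and Week 40 with its own failure rule.
- **Late Visit 399 records are lost.** The Day 785 window has no upper limit.
- **Type I error is inflated.** The loss described would weaken a true effect, and no inflation is shown.

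**Conclusion.** The point holds as a defect in the written rule. Followed literally, SAP 2.1 leaves a completer seen on Day 117 or later without a Week 16 value for H2 to H4, and the SAP does not say how that patient enters the analysis. The probable direction is dilution of a canakinumab benefit. The size is not known; the range of 4% to 31% of completers rests wholly on a normal spread with SD 2 to 7 days, and the low end would be of little consequence. A changed conclusion for H2 to H4 is possible but not shown, and no effect on H1, H5 or Visit 399 is shown. The text should be corrected before the Week 16 analysis, so that the choice between dropping, failing or keeping these patients is not made with results in view. Confidence in the textual fault is good; confidence in its practical impact is moderate.

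**What to change.** In SAP 2.1, restrict the Table 2-1 mapping to Visit 199, 299 and 399 records of patients who prematurely discontinued. For patients who completed the epoch, use the CRF visit number whatever the calendar day: Visit 199 as Day 113 (Week 16) and Visit 299 as Day 281 (Week 40).

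The cost is one sentence in the SAP and a small change to the visit-mapping program, with no new data. The downside is that some Week 16 values will have been taken a few days late.
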